### 5.4. Patient Disposition

Patient disposition will be summarized by cohort and overall. It will include a summary of the number and percentage of patients entered into the study, enrolled in the study, and treated, as well as number and percentage of patients completing the study (patients who receive  $\geq 1$  dose of study drug and have  $\geq 1$  post-baseline tumor assessment), or discontinuing (overall and by reason for discontinuation). Reason for discontinuation from both the study treatment and the study will be summarized by pre-determined categories.

### 5.5. Patient Characteristics

Patient demographics including age, race, ethnicity, country, screening height, weight and body surface area (BSA) will be reported using descriptive statistics.

Patient baseline disease characteristics including pathological diagnosis, disease stage, and Eastern Cooperative Oncology Group (ECOG) performance status will be summarized.

Patient preexisting condition, historical illness, prior anti-cancer therapies and other baseline characteristics such as smoking status will be summarized.

Patient characteristics will be summarized by cohort and overall.

### 5.6. Treatment Compliance

Treatment with prexasertib will be administered at the investigator site, therefore treatment compliance is assured.

### 5.7. Concomitant Therapy

All medications will be coded to the generic preferred name according to the current World Health Organization (WHO) drug dictionary. All concomitant medications will be summarized for the safety population using the preferred name by cohort and overall.

The use of analgesic medications will be summarized and listed, including dose, unit, frequency, and route of administration. Each analgesic may be analyzed according to the WHO pain ladder (WHO cancer pain relief, 1986) and/or the Analgesic Quantification Algorithm (AQA) (Chung et al. 2014). Additional exploratory analysis about the analgesic use may be conducted if deemed appropriate.

## 5.8. Post-Study-Treatment Therapy

The numbers and percentages of patients receiving post-study-treatment anticancer therapies will be provided by type of therapy (surgery, radiotherapy, or systemic therapy), and by drug class and/or name, overall and by line of therapy. The therapies will be summarized by cohort and overall for the safety population.

## 5.9. Efficacy Analyses

Efficacy analyses will be conducted on the ITT population and summarized by cohort. Efficacy analyses for interim analyses may be based on the safety population.

### 5.9.1. Primary Efficacy Analyses

**Overall response rate (ORR)** is defined as the number of patients who achieve a best overall response of complete response (CR) or partial response (PR) divided by the total number of enrolled patients per cohort. The ORR, with corresponding 95% exact CI, will be summarized for each cohort. The posterior estimates of ORR and posterior probability of ORR that is greater than the cutoff value will also be derived via a Bayesian model.

- Cohort 1, 2 and 3: posterior Pr (ORR>25%)
- Cohort 4: posterior Pr (ORR>15%)

**Disease control rate (DCR)** is defined as the number of patients who achieve a best overall response of CR, PR or stable disease for  $\geq 4$  months divided by the total number of enrolled patients per cohort. The DCR, with corresponding 95% exact CI, will be summarized for each cohort.

**CA-125 response** is defined as  $\geq 50\%$  reduction in CA-125 levels from a pretreatment sample. The response must be confirmed and maintained for  $\geq 28$  days according to GCIG criteria. Patients must have a pretreatment sample that is  $\geq 2$  times the upper limit of the reference range and obtained within 2 weeks before starting the treatment. The response rate based on CA-125, with corresponding 95% exact CI, will be summarized for each cohort.

**Progression-free survival (PFS)** is defined as the time from the date of enrollment until the first occurrence of documented disease progression per RECIST 1.1, or death from any cause in the absence of progressive disease (PD). Progression-free survival curves, median PFS, and PFS rates at 3 months intervals up to 12 months with 95% CI for each cohort will be estimated using the Kaplan-Meier (KM) method (Kaplan and Meier 1958).

If a patient is not known to have progressed or died at the time of analysis, PFS time will be censored at the last known progression-free assessment. The detailed censoring rules are described in [Table JTJN.6.1](#).

**Table JTJN.6.1. PFS events/Censoring Scheme**

Situationa	Event/Censor	Date of Event or Censor
Tumor progression or death	Event	Earliest date of PD or death
No tumor progression and no death	Censored	Date of last adequate radiological assessment or date of randomization (whichever is later) b
Unless		
No baseline radiological tumor assessment available	Censored	Date of enrollment
No adequate postbaseline radiological tumor assessment available and death reported after missing 2 scan intervals following randomization b,c	Censored	Date of enrollment
Tumor progression or death documented immediately after missing 2 or more scan intervals following last adequate radiological tumor assessment or enrollment (whichever is later) b,c	Censored	Date of last adequate radiological assessment or date of enrollment (whichever is later) b
New anticancer therapy started before tumor progression or death	Censored	Date of last adequate radiological assessment prior to the start of new anticancer therapy or date of enrollment(whichever is later) b

Abbreviations: CR = complete response; PD = progressive disease; PFS = progression-free survival; PR = partial response; SD = stable disease.

- a Symptomatic deterioration (that is, symptomatic progression that is not radiologically confirmed) will not be considered as tumor progression.
- b Adequate radiological tumor assessment refers to an assessment with one of the following responses: CR, PR, SD, or PD.
- c 2 scan intervals = 4 months.

**Duration of response (DoR)** is defined as the time from the date measurement criteria for CR or PR (whichever is first recorded) are first met until the first radiographic documentation of progression or death from any cause in the absence of PD. The analysis is for confirmed responders only. Median duration of response will be estimated using the KM method. The DoR will be censored according to the same rules as PFS.

**Overall survival (OS)** is defined as the time from the date of enrollment until death from any cause. If the patient is alive, lost to follow-up or withdrawn from study at the time of data analysis, OS data will be censored on the last date the patient is known to be alive. Overall survival curves, median overall survival, and survival rates at 6 months intervals up to 24 months with 95% CI for each cohort will be estimated using the KM method.

### **5.9.2. Sensitivity Analyses**

Patients are assigned to cohorts based on the local *BRCA* results. Sensitivity analyses of the efficacy endpoints may be done based on the centrally confirmed *BRCA* results. Other sensitivity analyses may be conducted if deemed appropriate.

## 5.10. Health Outcomes/Quality-of-Life Analyses

Patient reported outcomes data is being collected via a site and home-based device. The schedules of the health outcome assessments are summarized below. Daily collection of the Worst Pain NRS via the home device will be discontinued at progression or after Day 28 of Cycle 6, whichever comes first.

Questionnaires administered in clinic	Baseline visit	Administered on day 1 of each cycle, beginning with cycle 2	Short term follow-up
Worst Pain NRS	x		x
NFOSI-18	x	X	x

At home	
Worst pain NRS	Daily at bedtime

For each questionnaire, the compliance rate will be calculated as the number of completed assessments divided by the number of expected assessments. The compliance rate for the Worst Pain-NRS will be calculated at baseline, per week and per cycle, with reasons for non-compliance to be collected and reported for the baseline and short-term follow-up visit only. Additionally, the proportion of patients who have completed  $\geq 50\%$  of daily Worst Pain NRS assessments in the 7-day period prior to the first dose of each cycle and during each consecutive 7 day period post-baseline will be computed at each cycle. Patients will be considered compliant if they have completed  $\geq 50\%$  of the daily assessments during each period (e.g., week, cycle). The number of expected assessments for each period is the number of patients who have received last scheduled study drug before the scheduled assessment days (e.g., patients who have received Day 1 drug should be expected to complete all daily assessments before they receive Day 15 drug). For the NFOSI-18, the compliance rate will be calculated at baseline, each post-baseline visit (starting with cycle 2), with reasons for noncompliance to be collected and reported for all visits. The number of expected assessments at each post-baseline visit (starting with cycle 2) is the number of patients who have received study drug in a previous cycle.

For the Worst Pain NRS, a 7-day average of scores prior to the first dose of each cycle and a rolling 7-day average of scores regardless of dosing will be computed if  $\geq 50\%$  assessments are completed during each period. A 7-day average of scores based on any available data may be computed for sensitivity analysis even if compliance is less than 50%. For the NFOSI-18, the total score will be computed at baseline, each cycle (starting with cycle 2), and short term follow-up along with scores for the Disease Related Symptoms-Physical subscale, the Disease Related Symptoms-Emotional subscale, the Treatment Side Effects subscale, and the Function/Well-Being subscale.

Change from baseline for pre-specified concepts of interest (worst pain and NFOSI Total Score and Subscales) will be descriptively analyzed. For the Worst Pain NRS, change from baseline will be assessed in the 7-day average prior to the first dose of each cycle.

Time to deterioration in the total score as well as specific subscales and items in the NFOSI-18 is defined from the time of the patient's baseline visit to the time of the first increase in the respective score with confirmation at the next consecutive cycle or death from any cause, whichever comes first (a threshold characterizing meaningful worsening will be determined based on forthcoming psychometric analyses). Time to pain progression based on Worst Pain NRS and the weekly average of the worst pain scores will also be assessed. Median time to pain progression/deterioration with 95% CI for each cohort will be estimated using the KM method. Data for cohorts that have stopped early may not be analyzed. Correlation analysis between NFOSI pain item and the worst pain NRS will be conducted to account for lack of NRS data after cycle 6.

Data on analgesic consumption will be analyzed independently as well as in conjunction with PRO data from the worst pain NRS. For example, patients with pain progression based on worst pain NRS and their analgesic consumption will be summarized.

The association between PRO measures and efficacy outcomes may also be explored if deemed appropriate.

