	Adverse Events Collection/ CTCAE Grading		X				Collect throughout the study, CTCAE version 4.0; includes hospitalizations, emergency department visits, and/or occurrence of SBO.
Concomitant Medication Notation			X				Collect throughout the study; includes transfusions (platelets and RBC) and information on over-the-counter and prescription analgesics use.
Health Outcome Assessments	Worst Pain NRS		X				The patient will complete the single item worst pain NRS, at home immediately prior to bedtime every day. Collection of the Worst Pain NRS will be discontinued during study treatment at progression or Day 28 of Cycle 6, whichever comes first.
	NFOSI-18			X			The NFOSI-18 will be administered by site personnel prior to extensive interaction with site staff as well as administration of study drug on Day 1 of every cycle, beginning with Cycle 2.
Study Treatment	Prexasertib	X	X	X	X		Administer on Days 1 and 15 of every 28-day cycle, IV over approximately 60 (+10) minutes.

Note: Baseline/screening labs drawn within the indicated window of C1D1 may be used for both screening/baseline and C1D1 labs. Note that eligibility (including baseline/screening labs) must be confirmed prior to obtaining the biopsy and patient should fully recover from the acute effects of the biopsy prior to starting treatment.

Abbreviations: BSA = body surface area; CT = computed tomography; CTCAE = Common Terminology Criteria for Adverse Events; ECG = electrocardiogram; ECOG = Eastern Cooperative Oncology Group; EOI = end of infusion; IV = intravenous; NRS = numeric rating scale; NFOSI-18 = National Comprehensive Cancer Network – Functional Assessment of Cancer Therapy – Ovarian Symptom Index-18, PK = pharmacokinetics; QTcF = corrected QT interval using Fridericia’s formula; RBC = red blood cell; RECIST = Response Evaluation Criteria in Solid Tumors version 1.1 (Eisenhauer et al. 2009); SBO = small bowel obstruction.

Table JTJN.3. Post-Study-Treatment Follow-Up Schedule of Activities

	Study Period	Post-Discontinuation Follow-Up		Comments
		Short-Term Follow-Up ^a	Long-Term Follow-Up ^b	
	Duration	30 ± 5 days	60 ± 14 days	
	Visit	801	802-X	
Procedure Category	Procedure			
Physical Examination	Physical examination (including weight)	X		
	Vital signs	X		Includes blood pressure, pulse, and temperature.
	ECOG performance status	X		

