7.2.1. Selection and Timing of Doses

A cycle is defined as an interval of 28 days.

The actual doses of study treatment to be administered will be determined by calculating the patient's BSA at the beginning of each cycle. Although it is acceptable to recalculate more frequently, if the patient's weight does not fluctuate by more than $\pm 10\%$ from the weight used to calculate the prior cycle or from baseline, the BSA will not need to be recalculated. A $\pm 10\%$ variance in the calculated total dose will be allowed for ease of dose administration.

A patient may continue to receive study treatment until she meets 1 or more of the specified reasons for discontinuation.

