7.4. Dose Modification

The following rules should guide dosing:

- Before each dose:
 - Nonhematologic toxicities must resolve to Grade 0 or 1 or baseline, except AEs with no immediate medical consequence or those that can be controlled with adequate treatment (for example, pain, alopecia, fatigue, nausea, vomiting, or diarrhea)
 - Neutropenia and anemia must resolve to Grade ≤ 2 , and thrombocytopenia to Grade ≤ 1 , as shown in [Table JTJN.6](#).

Table JTJN.6. Hematologic Parameters Required Prior to Each Dose

	Dose
Neutrophils	$\geq 1000/\text{mm}^3$
Platelets	$\geq 75/\text{mm}^3$
Hemoglobin	$\geq 8 \text{ g/dL}$

- A delay of a dose due to holiday, weekend, inclement weather, or other unforeseen circumstances will be permitted for a maximum of 7 days and not counted as a protocol deviation.
 - Initiation of a dose may be delayed for a maximum of 14 days (28 days from prior dose) to allow a patient sufficient time for recovery from study treatment related toxicity (for example, a delay of 14 days from the planned Day 1 of the cycle). Note that if the Day 15 dose cannot be administered within 7 days of the planned Day 15 (e.g. 21 days from the prior dose (by Day 22), it should be omitted and the next dose administered 28 days of the prior dose as the start of a new cycle. In addition, if there is a persistent downward trend in the predose neutrophil/platelet counts a treatment delay may be considered.
 - In exceptional circumstances, a longer delay is permitted upon agreement between the investigator and the Lilly CRP/CRS. Dosing delay of study drugs due to non-study drug related AEs may be permissible if deemed clinically necessary by the investigator and following discussion between the investigator and the CRP/CRS. The interval between prexasertib doses must not be less than 14 days. If a dose is delayed (for toxicity or other circumstances), the next dose should be adjusted so that there is a ≥ 14 -day interval. If needed, the cycle length should be extended to accommodate the delay.
 - Dose adjustments and delays on either Day 1 or 15 will be made based on the clinical assessment of hematologic and nonhematologic AEs as shown in [Table JTJN.7](#). In addition, the dose can also be delayed or adjusted at the investigator's discretion as clinically indicated.

Table JTJN.7. Dose Adjustments and Delays

Toxicity	CTCAE Grade	Action	Dose Adjustments and Considerations

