### 5.2. Populations

The following analysis sets will be defined for this study:

**Intent-to-Treat (ITT) population:** will include all enrolled patients (i.e., patients have been assigned to a cohort). The ITT population will be used for all baseline, efficacy and PRO analyses.

**Per-Protocol population:** will include all treated patients who do not have any major protocol violations that could potentially affect the efficacy conclusions. This population will be used for efficacy and PRO sensitivity analyses.

**Safety population:** will include all enrolled patients who have received  $\geq 1$  dose of prexasertib, regardless of their eligibility for the study. This population will be used for all dosing/exposure, and safety analyses.

**Pharmacokinetic population:** will include all enrolled patients who have received  $\geq 1$  full dose of prexasertib and have baseline and  $\geq 1$  postbaseline evaluable PK sample.

**Biomarker population:** will include all enrolled patients from whom a valid assay result has been obtained.

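### The by-cycle change in worst pain leaves out the last cycle of any patient who stops before Cycle 7, so that summary is selected on receiving a further dose

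*SAP*

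**What the plan says.** SAP 5.10 fixes the window for the pain change summary: "For the Worst Pain NRS, change from baseline will be assessed in the 7-day average prior to the first dose of each cycle".

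The data collected are much denser. In the protocol's on-treatment schedule (Table JTJN.2), "The patient will complete the single item worst pain NRS, at home immediately prior to bedtime every day". SAP 5.10 adds that this home collection "will be discontinued at progression or after Day 28 of Cycle 6, whichever comes first".

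The same SAP section plans two other uses of the diary that do not require a further dose. First, "a rolling 7-day average of scores regardless of dosing will be computed", subject to a 50% completion rule. Second, "Time to pain progression based on Worst Pain NRS and the weekly average of the worst pain scores will also be assessed", estimated by Kaplan-Meier for each cohort. The SAP names no change-from-baseline summary for the rolling average.

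A clinic rating of worst pain is taken at baseline and again at the short-term follow-up visit after treatment stops. SAP 5.10 lists a follow-up score for the NFOSI-18 but names no change to follow-up for pain. SAP 5.3 rules out imputing missing scores. SAP 5.2 states: "The ITT population will be used for all baseline, efficacy and PRO analyses". The objectives tables class these patient-reported outcomes as tertiary/exploratory, and SAP 5.10 plans a descriptive analysis of change.

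**The concern.** A patient who stops during or at the end of cycle k never has a first dose of cycle k+1. Her ratings in cycle k then fall in no window and never enter change from baseline, however complete her diary is. SAP 5.10 still counts those days when it computes completion, because a rating is expected once the last scheduled drug has been given. The same ratings are thus expected for compliance but left out of the change summary.

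Whether a value enters therefore depends on something that happens after treatment starts: being dosed again. Patients stop for progression, toxicity or decline, and some of these reasons may go with worse pain. With no control arm, nothing offsets that selection. A flat or improving by-cycle pain curve could arise partly because patients with worsening pain had left it, and cohorts that stop at different rates would not be comparable. Protocol 9.10 makes worst pain one of two focal patient-reported concepts, so the summary is likely to be read.

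**Working it through.** The documents give no sample size, power or target figure for this endpoint, so there is no plan figure to reproduce. The check counts usable windows and then sizes the possible bias under stated assumptions.

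**Inputs from the documents.** Cycle length: "A cycle is defined as an interval of 28 days" (Protocol 7.2.1). Diary: daily, ending at progression or Cycle 6 Day 28. Pre-dose windows start before Cycle 2 (Protocol 10.3.3.9). First scan: about 8 weeks from Cycle 1 Day 1, which is the end of Cycle 2.

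**Step 1: windows per patient.** Assume no dose delays and a diary kept to the end of the last cycle. A patient whose last started cycle is k (1 to 6) has windows before Cycles 2 to k, so k − 1 windows. They use 7(k − 1) of 28k diary days. Weekly averages taken without reference to dosing would number up to 4k.

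| Last cycle started | Pre-dose windows | Diary days used | Share | Weekly averages possible |
|---|---|---|---|---|
| 1 | 0 | 0 of 28 | 0% | 4 |
| 2 | 1 | 7 of 56 | 12.5% | 8 |
| 3 | 2 | 14 of 84 | 16.7% | 12 |
| 4 | 3 | 21 of 112 | 18.8% | 16 |
| 5 | 4 | 28 of 140 | 20.0% | 20 |
| 6 | 5 | 35 of 168 | 20.8% | 24 |
| 7 or later | 6 | 42 of 168 | 25.0% | 24 |

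A low share of days is not itself the fault, since any pre-dose window samples one week in four. The fault is that every row up to 6 is one window short, and the missing one is always the last cycle. A patient stopped at the 8-week scan contributes only the window before Cycle 2. A patient who starts Cycle 7 on schedule has all six diary cycles represented.

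**Step 2: how many patients this touches (assumption).** Take time on treatment as exponential with median m months of 30.4375 days, so the share still being dosed at day d is 0.5^(d / (30.4375 m)).

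- No post-baseline change value = 1 − share at day 28. For m = 3: 1 − 0.81 = 19%. For m = 6: 1 − 0.90 = 10%.
- Last cycle lost = 1 − share at day 168. For m = 3: 1 − 0.28 = 72%. For m = 6: 1 − 0.53 = 47%.

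A second illustration uses the 60% disease control rate at 4 months in Group 2 of Study E001 (Protocol 3.2.2.3) as a rough proxy for being on treatment. The shares with a pre-dose window at Cycles 2 to 7 are then 89%, 79%, 70%, 63%, 56% and 49%. About 11% have no post-baseline value and about 51% lose their last cycle.

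**Step 3: size of the bias (assumption).** Among patients who start a given cycle, let f be the share who start the next one. Let D be the mean pain change in stoppers minus that in continuers. The mean over all starters is (continuers' mean) + (1 − f) × D. The pre-dose summary reports the continuers' mean alone, so it understates the mean pain change by (1 − f) × D. Under the exponential model f is the same for every cycle:

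- m = 3, f = 0.81: 0.19 × 1 = 0.19 and 0.19 × 2 = 0.38 points.
- m = 6, f = 0.90: 0.10 × 1 = 0.10 and 0.10 × 2 = 0.20 points.

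The range is about 0.1 to 0.4 NRS points per cycle. Progression found at the week-8 scan may cluster at the end of Cycle 2. That would make f lower there, and the bias larger, than a constant rate implies.

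**The case against.** The strongest reply is that this is an ordinary observed-case display of an exploratory endpoint, that the window has a reason, and that other pain analyses cover the gap.

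**The window has a reason.** The NFOSI-18 is given on Day 1 of each cycle with a 7-day recall, and Protocol 10.3.3.9 sets its 4-of-7 completion rule on the same days. The alignment also serves the planned correlation between the NFOSI pain item and the NRS. This stands, and it is why the pre-dose summary should stay.

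**Other pain analyses exist.** A reader might infer that the whole pain result is selected on further dosing. The SAP does not support that: time to pain progression uses the NRS and weekly averages and can draw on last-cycle ratings up to progression. But it shows when pain worsens, not by how much, so it does not replace the change summary.

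**Not every patient loses a cycle.** A reader might infer that each patient's last cycle is dropped, and so put the lost share at one over the mean number of cycles. Anyone who starts Cycle 7 on schedule loses nothing, so that formula overcounts.

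**ITT.** A reader might see a contradiction with the ITT statement in SAP 5.2. That statement says which patients are analysed, not which windows, so there is none. The label does not, however, tell the reader how few patients stand behind a late cycle.

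**Follow-up rating.** It is one clinic rating, but so is the baseline rating, so the two compare like with like. The gap is only that the SAP does not name the comparison.

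**Size and direction.** A reader might assume that half the patients do not continue after week 8, and so reach a bias of 0.5 to 1.0 points. Nothing in the documents supports that fraction. The direction is also undocumented: the protocol describes haematologic toxicity as the most frequent, and stopping for it need not mean worse pain.

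**Conclusion.** The point holds for one analysis. As written, the Worst Pain NRS change-from-baseline summary omits the last cycle of every patient who stops before Cycle 7, and it omits all post-baseline change for a patient who stops in Cycle 1. This follows from the SAP text and needs no assumption. Because scores are not imputed, each by-cycle figure is conditional on receiving a further dose.

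The size is not known. Exponential time on treatment (median 3 to 6 months) and a difference of 1 to 2 points between stoppers and continuers give about 0.1 to 0.4 points per cycle, perhaps more at the week-8 scan. Both inputs are assumptions. That the summary looks too favourable is plausible rather than shown.

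Ratings after progression are missing because collection stops, not because of this window, and no re-analysis recovers them. Severity is minor: the endpoint is exploratory and descriptive, and no decision rule depends on it.

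**What to change.** In SAP 5.10, keep the pre-dose summary for alignment with the Day 1 NFOSI-18 and add:

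*Change from baseline in Worst Pain NRS will also be summarised by consecutive 7-day period from Cycle 1 Day 1 to the end of home rating (progression or Cycle 6 Day 28), using the 7-day average computed regardless of dosing and the same ≥50% completion rule, with the number of patients contributing at each period. The change from baseline to the short-term follow-up visit rating will be reported separately.*

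A by-week summary is preferable to a single replacement window such as Days 22 to 28. For patients who stop mid-cycle, such a window would need a substitute that mixes post-infusion days with end-of-cycle days, and in delayed cycles it would no longer match the Day 1 NFOSI-18 recall.

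The cost is minor extra programming on data already collected, with no change to visits, dosing or patient burden. The pain result may look slightly less favourable.
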